11.5 Interim statistical analyses

In order to inform stakeholders on a regular basis interim analyses will be planned every Monday during the course of the study (whatever the number of new patients enrolled in the study).

Descriptive figures on the main endpoints such as hospitalisations, intensive care admissions, ventilations and death as well as the durations of each and the time to death will be provided.

As the analyses will only be descriptive, no correction for multiplicity will be applied.

12 QUALITY ASSURANCE AND QUALITY CONTROL (Monitoring)

The LIH will perform internal quality management of study conduct and data collection. Quality control (QC) procedures will be implemented from the beginning in the data entry system and data QC checks will be generated by the database.

12.1 Monitoring

In order to guarantee the authenticity and the credibility of the data in conformity with Good Clinical Practices, the sponsor has installed a quality assurance system that comprises:

- Conduct, management and follow-up of the trial according to the procedures of the CIEC of the Luxembourg Institute of Health : a Clinical Research Associate (CRA) will be designated as monitor within the CIEC team, this CRA will not have any other role on the project, and will monitor the study
- The quality control of the data of the investigator site by the monitor, whose role will be but will not be limited to :
 - to check the compliance with the clinical trial protocol, Good Clinical Practices (GCP) and local law requirements
 - to check the Informed Consent form and the eligibility criteria of each subject enrolled in the clinical trial
 - to check concordance and coherence of the data reported in the CRF against the source documents
 - compliance with data and samples collection reporting timelines
 - compliance with samples storage and shipment guidelines
 - to check that the samples stored on-site are under the appropriate conditions.

During monitoring visits, the investigator will provide direct access to all source documentation relevant to the subject's participation in the study.

It is the responsibility of the investigator to maintain adequate and accurate CRFs for each enrolled patient.

All personnel, bound by professional secrecy, must maintain the confidentiality of all personal identity or personal medical information.

The monitor will ask the investigator to modify any erroneous, forgotten or unclear data. All the modifications will be explained (if necessary), dated and signed.

12.2 Inspections and audits

To ensure compliance with clinical trial protocol, Good Clinical Practice and applicable regulatory requirements, the investigator and its institution should permit auditing by the sponsor or its representative.

The investigator agrees to allow the auditors to have direct access to all study records and facilities, being understood that auditors are bound to professional secrecy and as such will not disclose any personal identity or personal medical information. The investigator must maintain a comprehensive and centralized filing system of all study-related documentation that is suitable for inspection by auditors. The investigator agrees to participate in an audit conducted at a convenient time in a reasonable manner.

Government regulatory authorities may also perform inspections either during or after the study. In the event of an inspection by any regulatory authority, the investigator should promptly notify the sponsor. The investigator agrees to cooperate fully with inspections conducted by regulatory authorities and to allow representatives of the regulatory authority access to all study records. Inspectors are bound to professional secrecy, as such will not disclose any personal identity or personal medical information. The investigator will forward to the sponsor a copy of any inspection records received.

12.3 Source documents

Source documents provide evidence for the existence of the participant and substantiate the integrity of the data collected. Source documents are filled at the investigator's site. Data entered in the eCRF that are transcribed from source documents must be consistent with the source documents or the discrepancies must be explained.

13. REGULATORY, ETHICAL and OVERSIGHT CONSIDERATIONS

13.1 Informed Consent Process

Screening for eligibility

As mentioned above in the section "**Strategies for recruitment and retention**", there are two different ways to recruit the participants :

- When the information of a positive test returns to the Sanitary Inspection the patient (or his/her legal representative) is contacted by phone by a collaborator of the Sanitary Inspection. During this call, participants will be asked if they agree to be contacted by LIH for research purposes. The contact details of people who agreed will be communicated to LIH and these people will be contacted by phone by an experienced nurse or clinical research associate from the CIEC to explain them the study, collect the consent and organize the baseline visit if the participant agrees to participate in sample collection. Alternatively a letter will be sent with some information about the study and an invitation to contact the CIEC staff if they are interested in participating in this research project.
- For hospitalized patients, patient information and inclusion will be performed by the medical staff or by CIEC staff when possible.

Eligibility will be verified by the CIEC team and an inclusion visit will be organized at home or at hospital. During this initiation visit, the Informed Consent of the participant will be collected as described below.

Obtention of Informed Consent

Informed consent is a process that is initiated prior to a subject agreeing to participate in a clinical research study and continuing throughout the individual's study participation. The investigator, or another member of the investigating team (experienced nurse or clinical research associate from the CIEC), will discuss the study with the subject whereby the subject will be given the opportunity to understand the objectives, risks and inconveniences of the study and the conditions under which it is to be conducted. The language used to inform the subject, both oral and written, should be concise, described in layman's terms and should be understandable to the subject. Neither the investigator nor any member of the study team shall coerce or unduly influence a subject to participate or to continue to participate in a study.

In the present context of Covid-19 pandemic it's not possible for security reasons to have a fully paper consent form. Moreover it's important that the nurses spend a minimum of time in the house of the positively tested persons.

The study will therefore be explained to the potential participants by phone and an electronic version of the Subject Information Sheet (SIS) and Informed Consent Form (ICF) will be sent by email if the person is interested in the study participation.

Participants will have the possibility to participate only in the data collection or in both data and sample collection. In case the subject agrees to participate in data collection only, they will be asked to fill in the consent form electronically (e-consent).

If the subject also agrees to participate in the sample collection, they will be asked to fill in the e-consent and a paper version for the sample collection will be brought by the nurse at baseline visit to fill in this part and obtain a written signature so that the nurse can answer additional questions if necessary. The paper document will be given to the participant and a photo of the document will be stored at LIH.

The subject will have sufficient reflection time between the first contact (description of the study via phone) and the sample collection visit. In addition, the subjects will have the opportunity to ask any question during the phone call or by email, before signing the electronic Informed Consent Form.

Alternatively, if the participant does or can not want to receive the documents by email, the nurse in charge of the inclusion visit will bring directly a paper version of the documents, answer the potential questions and ask the participant to complete and sign the form during the visit.

The informed consent of all persons willing to participate in the study will be collected, while two different SIS and ICF will be given to the subjects, according to the cohort they will belong to (Precovid for subjects with a positive COVID-19 test and Precovid H for the persons adults, living in the same household).

Finally, the subject will be informed that he/she can withdraw from the study at any time, without giving any reason and without any consequences on his/her medical care.

ICFs will be approved by the competent authorities, and the subject will be asked to read and sign the consent form prior to starting any procedures being done specifically for this study. In exceptional cases, when the subject is presented with acute conditions and unable to receive and understand the information about the study, the Informed consent can be first requested from the next relative and from the subject as soon as this becomes possible.

The written ICF must be dated and personally signed by the principal investigator or delegates and the subject giving consent (or next relative in case of emergency situation).

The electronic copy (photo) of the signed ICF will be retained in the study file (ISF) at LIH and will be made available for monitoring, audit or inspection.

No compensation will be offered to the subjects for their participation.

Specificities for participants between 0-17 yrs :

All participants should meet the inclusion criteria and none of the exclusion criteria.

Legal representatives of all subjects between 0-17 years will receive all the required information through the Study Information Sheet and the Informed Consent Form to decide whether or not to allow their child to participate in

the study. He/she will also have the possibility to contact the study team to ask questions related to the study. The children of 10 years or older are invited to give their assent via the Assent Form.

13.2 Ethics Committee/Competent Authority

The study will be submitted by the Luxembourg Institute of Health, in accordance with the local regulations, in particular the 8th MARCH 2018 LAW ON HOSPITALS (Art 27), to and authorized by the Health Minister, after requesting the opinions of the Health Directorate (Direction de la Santé) and the National Research Ethics Committee (Comité National d'Ethique de Recherche).

The principal investigator and the sponsor ensure that the study is conducted in full conformance with the principles of the "Declaration of Helsinki" 1964, as revised from time to time and with the laws and regulations of Luxembourg, whichever affords the greater protection to the individual. The study fully adheres to the principles outlined in "Guideline for Good Clinical Practice" ICH-E6 Tripartite Guideline (January 1997) and with national laws.

The principal investigator ensures compliance with the national laws, the ICH GCP and with the EU General Data Protection Regulation (GDPR) with regard to the processing of personal data (GDPR) and the law of 1 August 2018 on the organization of the national commission for data protection and the general regime on data protection.

13.3 Communication strategy

A newsletter will be prepared periodically (3 or 4 times per year) by the Predicovid team and provided to the study participants. With this newsletter, we aim to inform participants and the public about the progress of the project and keep them motivated to complete the monthly questionnaires. The newsletter will contain an editorial, news including research findings from the Predicovid study and sub-studies linked to the project, infographics about the status of the cohort, answers to frequently asked patient questions or portraits and descriptions of people working in the Predicovid team.

[figure not shown]
The newsletter will be in an electronic format and will be sent by email to the study participants by the CIEC team to safeguard their privacy.

To ensure a high participation rate in the completion of the last monthly questionnaire, participants will also receive some reminders by phone or email (max 2 emails and 2 phone calls).

A website dedicated to the study will be developed to inform the general public and the scientific community about the PredCovid study and its sub-studies. The content of the newsletter will be available on this website but also scientific articles related to the study more dedicated to researchers or physicians.

14. CONFIDENTIALITY AND PRIVACY

Predi-COVID Architecture

Personal data includes the following information:

- information that identifies the subject directly (such as his/her name, address, telephone number);
- the age and sex of the subject;
- information relating to the subject's state of health, including medical history;
- the subject's medical treatments and his/her response to medical treatments;
- information about the subject's biological samples and the results of analyses performed on these;
- information about the subject's medical images and the results of the evaluation of these.

In every step of data collection, data storage and data access across the Information System of this study, personal data will be processed in compliance to the General Data Protection Regulation (GDPR) of 27 April 2016 in the respect of Data Subjects' privacy by design and by default principles.

Each software used by the different actors during the processing of patients' personal data will require nominative accounts. These accounts will be managed by LIH to be sure that each person only access authorized data for a specific purpose (data partitioning), directly related to the current study. Each software has its own security rules: pseudonymization of data subsets wherever possible, encryption of sensitive data, etc.

In his role of sole controller of this activity, LIH will need to manage the administrative data of the patients included in his study in order to be able to collect their consent, give them access to the different software to collect data and be able to visit them to collect biosamples as well.

The patients may not be in sufficient dispositions to be able to fully accept or refuse and his or her consent could not be considered as being freely given, specific, informed and unambiguous, especially those recruited when at the hospital. It is therefore essential that the Ministry of Health supports LIH in this activity among the population as well as healthcare professionals to be able to contact those patients before having their initial consent.

All Covid-19 positive people are contacted in the context of the national follow-up by the Sanitary Inspection and will be asked if they agree to be contacted by LIH for research purposes. If yes, and once his or her formal consent is obtained, LIH will implement a pseudonymization by application so that only LIH can match information from different sources (CRF, CoLive LIH application): patient tracking applications and additional clinical data collection applications either at the hospital or at the patient's home.

The corresponding matrix table – containing the correspondence between the administrative data of the patient and the different pseudonymes – will be kept at LIH in a secured environment (Ennov Clinical) by authorized persons only related to that study. This table will be kept on a physically separate server from the clinical and epidemiological data to minimize the risk of reidentification.

Each time a new patient will be entered in any of the relevant software to collect his or her data, LIH will be responsible to provide the user of this software with the pseudonym (either the GP, a nurse or the patient himself or herself).

The primary legal basis for this study will be the patient's consent (Article 6.1 a) and Article 9.2 a) of the GDPR) as described in paragraph 14.1 above.

Therefore, Luxembourg Institute of Health will be the sole-controller for this activity.

The following actors are considered as Data Provider: patients themselves and healthcare professionals whether at the hospital or outside hospitals. The LNS and certified laboratories via the central platform eSanté will be the initiators of the process for positive patients for COVID-19 and therefore considered as Data Providers as well.

Each actor will only have access to a sub-dataset according to his or her role in the activity (minimization and partitioning principles). The study team only at LIH will have access to all pseudonymized datasets in order to execute its missions in the frame of this activity.

Transfer to third party

Some recipients of the data may be located outside your country and outside the European Economic Area (United Kingdom, for example). These may be countries whose level of data protection has not been confirmed by the European Commission as adequate. In this case, security measures equivalent to the security measures required by Luxembourgish and European regulations will be taken in order to protect subject rights in terms of data confidentiality, by entering into specific contractual agreements.

Storage of encoded data

For adults, encoded data will be kept for 15 years after the end of the study. However, 5 years after the end of the study, nominative data and the correspondence table between the identifying data and the study number will be deleted.

For minors, encoded data will be kept for 20 years after the end of the study. A dynamic management of the correspondence table will be retained to allow each person who attained the age of majority to consent to the secondary use of his/her data. On a case-by-case basis, each nominative data will be deleted from the table of correspondence after re-consent or refusal if any.

Subject rights related to personal data

The subject may exercise the following rights related to his/her personal data:

- Request information about the processing of data about him/her.

- Request the correction of the data about him/her if they are incorrect or incomplete. In certain cases (in accordance with the conditions set out by the law), the subject has the right to restrict the scope of his/her data processing.
- Retrieve his/her personal data and transfer then to a third party.
- Withdraw his/her consent at any time without giving a reason.

Lastly, the subject has the right to lodge a complaint with Luxembourg's National Commission for Data Protection (CNPD) in relation to the processing of his/her personal data.

15. FINANCING AND INSURANCE

The study is financed by LIH. Additional funds will be further requested to the FNR. The sponsor has subscribed to an insurance policy (Zurich Insurance plc, Belgium Branch, [name]) in compliance with local laws, covering its responsibility for all the participants for any injury that might be caused by the clinical trial.

16. STUDY CLOSURE

The end of study is declared when all the following criteria have been met:

- 12 months after inclusion of the last subject .
- The data monitoring is closed and all queries are answered, meaning the database is mature for the analysis of the endpoints as defined in the protocol.
- The database has been fully cleaned and frozen for all analyses.

The relevant documents including Electronic Data and other patient records, should be retained after the end of the study until result publication and then will be stored at least for 15 years following LIH standard procedure for archiving.

The end of the study will be reported to the Ministry of Health and to the CNER within 90 days following the end of study.

The end of study report will be prepared and will be available for health authorities within one year after the end of the study.

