| Intervention | For every adult (a "case") tested positive by RTqPCR, up to 45 mL of blood will be taken, a nasal swab and an oropharyngeal swab will be performed, an induced sputum (or saliva), hair sample and a stool samples will be recovered at the inclusion. As follow-up, 6 months, 15 months and 24 months after inclusion, the same sampling will be performed. Two additional sampling visits will be proposed to adult participants with a reinfection or a post-vaccination infection at 3 weeks and at 2 months. For every child tested positive by RTqPCR, up to 50 mL of blood will be taken, a nasal swab, oro- and naso-pharyngeal swabs, induced sputum or saliva, hair sample, as well as a stool sample will be obtained at inclusion. The follow up visits at 6, 15 and 24 months after inclusion, will include the same samples. For patients at home, an experienced nurse from CIEC will perform the sampling, using all the required precautions and protections in the actual context. For hospitalised patients, a simplified sampling strategy will be put in place and adapted to the patient state, the workload of staff and adapted constantly depending on the evolution of the epidemy. Below is described the maximal sampling strategy. |
| Study timelines | 
 ● Recruitment period: up to 29 months (March 2020-August 2022) - to be adapted to the evolution of the epidemiological situation) First patient in: March 2020 ● Follow-up period : max 24 months ● Analysis of results and study report: 3 months ● Global duration: 54 months (to be adapted on the duration of the epidemiological situation) |
| Population | Predi-COVID Inclusion criteria: |

| | |
|--|---|
| | 
 • Signed informed consent form • Adult (≥ 18 years old), child and adolescent (0-17 years old) patients with confirmed SARS-CoV-2 infection as determined by PCR, performed by one of the certified laboratories in Luxembourg • Hospitalized or at home 
Exclusions criteria :
 
 • Patients not understanding French or German • |
| Patient withdrawal criteria | Transfer outside Luxembourg if no information can be collected in the receiving country. |

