2.4 Long-term consequences of Covid-19

Given the current body of knowledge, **there are key unsolved questions around the long-term (beyond 3 weeks) health consequences of Covid-19**, which in the absence of any consensus has been termed as “Long Covid” or “Long Haulers” in recent publications[14]. Also named **Chronic Covid Syndrome (CCS)**, this condition needs to be better described and understood. So far, it has been shown that a fraction of the Covid-19 patients who undergo a variable acute symptomatic phase of the disease are coming forward with continuing effects of the disease, with complaints such as mental fog, delayed latent periods in recalling events of recent past, tachycardia, extreme fatigue, inability to perform daily physical tasks[15]. The signs and symptoms are so diverse and related to multiorgan and systems that it is challenging to ascribe it a proper terminology[16]. It has also been recognized that there are Covid-19 affected patients in which renal, cardiac, neural, gastrointestinal, and coagulative features

dominate and threaten the life of the patients[17]. That being said, the majority of the data come from hospitalized patients and few studies report long-term health consequences of asymptomatic or mildly symptomatic forms of Covid-19. However it has been shown that a vast majority of patients with home based recovery had frequent cardiac inflammatory involvement, which was similar to the hospitalised subgroup with regards to severity and extent[18]. A call for more research has been recently released by doctors in the BMJ[19].

Only some of the above-mentioned long-term health related consequences of Covid-19 are covered in the monthly questionnaire in Predi-COVID. The last monthly questionnaire at the end of the follow-up (month 12) has been more detailed, to collect complementary information on a large spectrum of chronic conditions or symptoms potentially related to Covid-19 to increase the value of the Predi-COVID cohort study and associated spin-off projects.

To align with new research questions around Long Covid and its long term presentation, the total follow-up duration for participants has been extended to 2 years, with Long-Covid specific questionnaires at months 15 and 24 for all participants and a new biological sampling at 15 and 24 months.

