3.2 Secondary objectives

Secondary objectives include

- to study the long term (up to 2 Year) health consequences of COVID-19.
- to characterise clinical symptoms and biological markers for individuals with re-infection/infection post-vaccination and Long COVID
- to describe the trajectories of symptoms after being positively diagnosed to COVID-19
- to identify vocal biomarkers associated with respiratory syndromes, fatigue, anxiety or emotions related to COVID-19 which could then further be used for easy remote monitoring of COVID-19 patients.
- to identify the virological factors and the individual characteristics involved in viral escape to COVID-19 vaccines and in reinfections
- to characterize the cellular and antibody responses (type and durability) elicited by vaccines and in uninfected and recovered COVID-19 patients (either vaccinated or not) with an emphasis on the variability of immune responses

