8. PARTICIPANT DISCONTINUATION/WITHDRAWAL

Participant Discontinuation/Withdrawal from the Study

Patients can leave the study at any time for any reason if they wish to do so without any consequences. In this case, the data and samples already used for the study cannot be destroyed.

The subjects enrolled in the study in the Predi-COVID-H cohort (living with positively tested subjects) will be discontinued after 1 week if they returned seronegative results AND are symptom free one week after the inclusion in the study.

Lost to Follow-Up

Participants will receive questionnaires during the 12 months of the study except if they explicitly ask not to be contacted any more. Lost to follow-up participants are those who will not answer any of the questionnaires after baseline.

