10 DATA MANAGEMENT

Data will be collected through 3 different ways:

- 1/ Questionnaires using the ePRO module of Ennov Clinical: health status monitoring data with daily questionnaires during the 14 first days following diagnosis, then weekly questionnaires at weeks 3 and 4 and monthly questionnaires from month 2 to month 12. A unique link to the questionnaires will be sent by email to participants which will fill in the questionnaire online. Participants can choose to answer or not to the questionnaires. For children > 10 years, adapted questionnaires will be filled in directly by the child. For children < 10 years, no questionnaires will be sent.
- 2/ Adapted ISARIC CRF : at hospital and at inclusion for patients included from home. For patients at home data collection will be performed by phone by the CIEC team.
- 3/ CoLive LIH smartphone application (LIH in-house solution): innovative data (voice recordings and mini-questionnaires). For adults and children > 10 years.

Data in the ISARIC adapted CRF will be completed by a trained nurse or CRA from CIEC. Access to source data during hospitalisation will be provided by the different participating hospitals and/or by the e-santé national database. Data collection is the responsibility of the clinical trial staff at the site under the supervision of the site investigator. The investigator is responsible for ensuring the accuracy, completeness, legibility, and timeliness of the data reported.

In the e-questionnaires and the CoLive-LIH application, the patient will be responsible for the data entry.

Each data collection tool (e-questionnaires, ISARIC, CoLive LIH) implements its own data collection rules and controls, to ensure that data is entered correctly at the earlier stage of the data handling process. Each variable input will be controlled as soon as it is entered by the authorized user with allowable values, min and max values when necessary, consistency controls between relevant variables, allowable values filtering according to the context already fulfilled, etc.

Data handling will be carried out through specific edit checks to test the consistency of the database. Quality controls will also be regularly performed according to the clinical and epidemiological good practice guidelines.

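### Section 16 lets the study close 12 months after the last inclusion, although follow-up was extended to 24 months with M15 and M24 assessments

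*Protocol*

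**What the plan says.** The 24-month horizon appears in these places:

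- Synopsis, study timelines: "Follow-up period : max 24 months". The synopsis also places the detailed long-COVID questionnaire at M12, M15 and M24 and repeats sampling at 6, 15 and 24 months.
- Section 2.4: "the total follow-up duration for participants has been extended to 2 years". The M15 and M24 questionnaires are there meant for every participant.
- Section 3.2, first secondary objective: "to study the long term (up to 2 Year) health consequences of COVID-19".
- Section 7.1 has 15- and 24-month visit columns, and section 9 refers to PCR results at visits at 6, 15 and 24 months.

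The 12-month horizon, or a schedule without M15 and M24, appears here:

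- Section 16: "The end of study is declared when all the following criteria have been met", of which the only dated one is "12 months after inclusion of the last subject". The other two are closed monitoring with a database mature for the protocol's endpoints, and a cleaned and frozen database.
- Section 8: "Participants will receive questionnaires during the 12 months of the study".
- Section 10: "monthly questionnaires from month 2 to month 12", with no mention of M15 or M24.
- Section 5: evaluations up to 12 months, with sampling at baseline and 6 months.
- Section 6: a basic scheme of two sampling visits, at baseline and 6 months.

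The synopsis gives "Global duration: 54 months", with recruitment of up to 29 months (March 2020 to August 2022) and 3 months for analysis and report.

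**The concern.** The extension to two years reached the objectives and the visit schedule but not the closure rule or several operational sections. A team working from sections 5, 8, 10 and 16 could close the study correctly, by those sections, while M15 and M24 assessments are still due.

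Any such loss would depend on calendar time of inclusion. The last people enrolled would lack the late assessments, and the two-year objective would be answered disproportionately from those enrolled earlier. Data not collected at M24 cannot be recovered afterwards.

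The end-of-study date also starts other clocks: the 90-day notification and one-year report (section 16), and the deletion of adults' identifying data five years later (section 14).

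**Working it through.** **Inputs.** Recruitment R = 29 months (synopsis), or 30 if March 2020 and August 2022 are both counted in full. Follow-up F = 24 months and analysis A = 3 months (synopsis). Closure C = 12 months after the last inclusion (section 16). Visits at v = 12, 15 and 24 months (synopsis, section 7.1).

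**1. The plan's own total.** Duration = R + F + A.

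| Reading | Months |
|---|---|
| 29 + 24 + 3 | 56 |
| 30 + 24 + 3 | 57 |
| 30 + 24, analysis left out | 54 |
| 29 + 24, analysis left out | 53 |
| 29 + 12 + 3 (12-month closure) | 44 |
| 30 + 12 + 3 (12-month closure) | 45 |

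The stated 54 is reached only with 30 months of recruitment and no analysis period. Read as a total of all three components, it leaves 54 − 29 − 3 = 22 months after the last inclusion (21 with R = 30). That fits neither the 12-month closure rule nor a full 24 months.

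**2. Who reaches each visit at the earliest permitted closure.** Earliest closure = R + C = 29 + 12 = month 41. Visit v is reached only by those enrolled by month 41 − v, so the lost window is R − (41 − v) = v − 12 months.

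| Visit | Last enrolment month that reaches it | Window lost |
|---|---|---|
| M12 | 41 − 12 = 29 | none |
| M15 | 41 − 15 = 26 | last 3 months |
| M24 | 41 − 24 = 17 | last 12 months |

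With R = 30, closure is month 42, the cut-offs are months 30, 27 and 18, and the lost windows are the same. For recruitment ending in August 2022, M24 is lost from about August 2021 and M15 only from about the end of May 2022.

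**3. Share of participants.** The protocol gives no accrual curve. Assuming even accrual:

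- M24: 12/29 = 41% (12/30 = 40%).
- M15: 3/29 = 10% (3/30 = 10%).

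To show the sensitivity with R = 29, suppose the monthly rate in the affected window is half or twice that of the preceding months (an illustration, not a figure from the protocol):

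- M24: half, 6/(17 + 6) = 26%; twice, 24/(17 + 24) = 59%.
- M15: half, 1.5/(26 + 1.5) = 5%; twice, 6/(26 + 6) = 19%.

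The windows follow exactly from the text. The shares do not.

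**4. Do the other two criteria protect the visits?** The maturity criterion refers to endpoints defined in the protocol. Section 4 lists hospitalisation, intensive care, ventilation, transfer, clinical severity, death and laboratory measures, with no M15, M24 or long-COVID endpoint. The freeze criterion has no date. All three can therefore be satisfied with M15 and M24 data outstanding.

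**5. After the change.** With C = 24, the last M24 assessment falls at month 29 + 24 = 53 (54 with R = 30), or month 56 (57) including analysis. No enrolment window loses M15 or M24.

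**The case against.** The strongest defence is that section 16 requires all three criteria, so 12 months is a minimum. A team that follows section 7.1 and delivers what section 2.4 promises would lose nothing. This stands: a reader might infer that the study must stop at 12 months or that the two-year objective cannot be met, and the text supports neither. It does not remove the problem, because nothing in section 16 requires waiting for M15 or M24.

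The 24-month wording can also be read as a ceiling that allows shorter follow-up for late enrolees. Section 2.4 closes that route for the questionnaires by giving M15 and M24 to all participants.

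Other stronger readings also fail:

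- Loss is not total for those included after about August 2021. Most of that group keeps M15, and all keep M12.
- Two-year data would not come from the first waves only. At the earliest closure, 17 of 29 enrolment months still reach M24.
- Post-vaccination infections and reinfections may be more frequent among late enrolees, since the synopsis says no vaccine existed in March 2020. The protocol gives no counts over time, so their concentration in the lost window is not shown.
- The sampling loss concerns the sub-sample only, sampling is optional, and children under 10 receive no questionnaires.
- Section 10 describes the monthly questionnaires and omits M15 and M24. It does not say that collection stops at M12.

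On duration, the components are ceilings and the total is adaptable, so 56 is not the only defensible figure. What remains is that 54 does not equal the sum of the listed components.

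**Conclusion.** The protocol contradicts itself on when the study may end. Section 16 permits closure, without forcing it, up to 12 months before the last participants complete the adopted follow-up. At the earliest closure, those included in the last 12 months of recruitment would lose M24, and those in the last 3 months would also lose M15. About 40-41% and 10% apply only under even accrual over 29 to 30 months; the true shares could be lower or higher.

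The exposure is to the two-year secondary objective. The principal objective concerns severity, and none of the main criteria in section 4.1 is tied to M15 or M24. The correction still matters because the loss would be irrecoverable and related to enrolment date, and preventing it takes only wording. The 54-month figure is a separate, smaller inconsistency, 2 to 3 months short of the listed components.

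**What to change.** - **Section 16:** set the time criterion at 24 months after inclusion of the last subject, defined by the last M24 questionnaire or visit, and place the final database freeze after it.
- **Sections 5, 6, 8 and 10:** align follow-up length, questionnaire times and sampling visits with the M12/M15/M24 schedule in the synopsis and section 7.1, keeping sampling limited to the sub-sample.
- **Synopsis, study timelines:** reconcile the 54 months with its components. State whether recruitment counts as 29 or 30 months and whether the 3-month analysis is included (56 or 57 with it, 53 or 54 without).

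This adds no procedure, visit or sample beyond those already scheduled. The cost is a protocol amendment, and a final freeze and end-of-study report up to 12 months later than section 16 now allows (month 53 rather than 41, or 54 rather than 42).
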